#### 8.3.6 Secondary Endpoint- Mortality

Descriptive statistics will be used to analyze the effect of wearable defibrillators on 180-day and 360 day mortality following discharge from HF. Kaplan-Meier curves and survival analysis will be performed both for aggregate mortality and independently for sudden and non-sudden cardiac deaths. Cause of mortality will be adjudicated by a committee independent of the sponsor. The influence of baseline characteristics and EF recovery status on mortality will be evaluated. Comparisons will be made using the Seattle Heart Failure model as a predictive tool of post-discharge mortality.

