## 1.1 Background

#### 1.1.1 Sudden Cardiac Death in Heart Failure

Sudden cardiac death (SCD) is usually defined as death from a cardiac etiology within an hour of the onset of symptoms in a person who otherwise appeared in a stable clinical state. These deaths are often attributed to a cardiac arrhythmia, of which ventricular fibrillation is the most common. In the United States, SCD is the leading cause of death accounting for nearly 350,000 deaths per year or approximately 1,000 deaths per day. Although a preexisting heart condition may not be present, patients known to have heart failure (HF) have been shown to have a higher risk of SCD. Among patients with HF, those with ventricular dysfunction as evidenced by a lower left ventricular ejection fraction (LVEF) have a particularly high risk of SCD.

Over one million hospital admissions for acutely decompensated heart failure occur annually in the USA and one in nine death certificates list heart failure as a related cause. Within the Veterans Affairs Health Care System, mortality after discharge has declined but remains significant (over 10% at 90 days post-discharge in 2006), and re-admission rates have trended higher (over 6% at 30 days in 2006). Similar data has been reported among Medicare recipients. Sudden cardiac death may account for half of the cardiovascular mortality experienced.

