3.3.1 SCA/SCD, Sustained Ventricular Arrhythmias, and Mortality

3.3.1.1 "Sudden Cardiac Death" will be defined as an unexpected, non-traumatic, non-self-inflicted fatality in otherwise stable subjects who die within one hour of the onset of the terminal symptoms. Subjects dying more than one hour after a sudden cardiac arrest (SCA) from a ventricular arrhythmia will be designed as non-sudden death due to ventricular arrhythmia. For unwitnessed deaths participants will meet the definition of sudden cardiac death if they are found dead within 24 hours of being well, assuming there is no evidence of another cause of death during that time period. Autopsy results may be used when available.

For the mortality analysis, all deaths will be classified by the site investigator as cardiac or non-cardiac, and sudden or non-sudden.

- 3.3.1.2 "Appropriate detection" will be defined as a device alarm/detection during a ventricular tachyarrhythmia.
- 3.3.1.3 "Sustained ventricular arrhythmia" will be defined as any WCD-recorded appropriate detection with ≥ 30 seconds of uninterrupted VT/VF.
- 3.3.1.4 "Appropriate treatment" will be defined as a therapy shock or anti-tachycardia pacing (ATP) given during a ventricular tachyarrhythmia.
- 3.3.1.5 "Inappropriate treatment" will be defined as a therapy shock and/or ATP (for ICD recipients) delivered in the absence of an appropriate detection.
- 3.3.1.6 "Other treatment" will be defined as a therapy shock delivered during an appropriate detection but on a section of the recording not showing a ventricular arrhythmia.
- 3.3.2 Effectiveness of the wearable defibrillator in treating ventricular arrhythmias

Clinical outcomes and device data from any defibrillation or cardiac event will be reviewed for success as defined by appropriate detection and defibrillation, conversion out of the detected ventricular arrhythmia, and consciousness when medically evaluated after treatment.

- 3.3.3 Incidence of other WCD recorded arrhythmias, such as asystole and supra-ventricular arrhythmias.
- 3.3.4 Economic and healthcare utilization data on all patients

Information (days, reasons) on any hospitalizations, emergency room visits, observation stays, urgent care visits, other physician office visits, and stays at skilled nursing facilities.

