## 6.4 Long-term Clinical Outcome Assessment

Final survival assessment will be 1 year from WCD start of use, ± 14 additional days.

6.4.1 Sites will be asked to determine survival for all patients enrolled in the study through either routine medical records and appointments, or a phone call to the patient.

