#### 8 Statistical Plan

#### 8.1 Sample Size and Power Calculation

The total number of WCD prescriptions for the study is estimated to be 868, and assuming ~15% lost follow up, 738 patients will have an EF measurement at day 90. The sample size was calculated using data-based estimates as described below.

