#### 8.4 Statistical Methods

All analyses have been described elsewhere in the protocol.

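### Cause-specific Kaplan-Meier curves in 8.3.6 would by default overstate the actual risk of sudden and of non-sudden cardiac death; cumulative incidence should be used (minor)

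*Combined protocol and SAP*

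**What the plan says.** Section 8.3.6 of the combined protocol and SAP plans Kaplan-Meier curves and an unspecified survival analysis "both for aggregate mortality and independently for sudden and non-sudden cardiac deaths". It does not say how a death from another cause enters a cause-specific curve. Section 8.4 adds no method: "All analyses have been described elsewhere in the protocol". Competing risks, cumulative incidence and cause-specific hazards are not mentioned anywhere in the plan.

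The cause categories are in section 3.3.1.1: "all deaths will be classified by the site investigator as cardiac or non-cardiac, and sudden or non-sudden". Non-cardiac death is therefore a recorded category. It counts in aggregate mortality, but 8.3.6 gives it no curve. The horizon is in section 6.4: "Final survival assessment will be 1 year from WCD start of use", with a 14-day window. The analysis is descriptive and belongs to a secondary endpoint.

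**The concern.** A patient who dies of pump failure or of a non-cardiac cause cannot later die suddenly. If that death is treated as censoring, the Kaplan-Meier estimator behaves as though the patient stayed at risk of sudden death after the last observed day. Its complement then answers a hypothetical question: what share would die suddenly if no other death were possible? A reader of the study report will want the share of patients who actually die suddenly. The first quantity is never smaller than the second, and a larger sample or better follow-up does not close the gap.

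Sudden death is central to the rationale for the device, so its reported risk should carry its plain meaning. The gap also widens as mortality rises. If curves by cause are compared between groups with different mortality, for instance by the EF recovery status that 8.3.6 proposes to examine, the overstatement will differ between the groups.

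**Working it through.** The plan gives no cause-specific mortality figure, so there is nothing to reproduce. The check asks how far apart the two estimators lie over a plausible range.

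**Inputs**
- From the documents: one-year horizon (6.4); sudden death as about half of cardiovascular deaths (1.1.1: "Sudden cardiac death may account for half of the cardiovascular mortality experienced"); up to 600 study patients and up to 1400 registry patients (Study Summary).
- Assumed, because not given: total one-year mortality T of 5%, 10%, 20% and 34.4%; non-cardiac share of deaths c from 0% to 40%; constant hazards; cardiac deaths split evenly.
- The top value of T extends the external figure in 1.1.1, "over 10% at 90 days post-discharge in 2006", at a constant rate over four 90-day periods: 1 - 0.9^4 = 34.4%. It serves as an upper bound, not as an expectation for this cohort.

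**Formulas**
- Total cumulative hazard: H = -ln(1 - T).
- Share of deaths that are sudden cardiac: w = (1 - c)/2, and the same for non-sudden cardiac.
- Kaplan-Meier complement with other causes censored: 1 - exp(-wH).
- Actual cumulative incidence (what Aalen-Johansen estimates): wT.

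**Worked case, T = 10%, c = 20%**
- H = -ln(0.9) = 0.1054 and w = 0.4.
- Kaplan-Meier complement: 1 - exp(-0.4 × 0.1054) = 4.13%.
- Cumulative incidence: 0.4 × 10% = 4.00%.
- Relative overstatement: about 3.2%.

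**Range** (columns 2, 3, 5 and 6 use c = 20%; column 4 runs c from 0% to 40%)

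| T | Sudden, 1-KM | Sudden, cumulative incidence | Relative overstatement | Sum of the two planned 1-KM | Sum of 1-KM over all three causes |
|---|---|---|---|---|---|
| 5% | 2.03% | 2.00% | 1.3-1.8% | 4.06% | 5.08% |
| 10% | 4.13% | 4.00% | 2.6-3.7% | 8.25% | 10.34% |
| 20% | 8.54% | 8.00% | 5.6-7.9% | 17.1% | 21.4% |
| 34.4% | 15.5% | 13.8% | 10.5-15.1% | 31.0% | 39.1% |

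The absolute overstatement runs from about 0.03 percentage points (T = 5%) to about 1.8 (T = 34.4%, c = 0).

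**Do the curves add up?** With no tied deaths, the product of the Kaplan-Meier curves over all causes equals the overall curve. The complements summed over all causes are therefore at least total mortality, as the last column shows. A sum over only some causes need not be. The two planned curves sum to more than T only if c is below 1 - 2 ln(1 - T/2)/ln(1 - T). That threshold is about 1.3%, 2.6%, 5.6% and 10.5% for the four values of T.

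**Simulation** (1000 runs per setting, 15% random loss over the year). The plan's own "assuming ~15% lost follow up" applies per 90-day interval; the figure is borrowed here only to introduce some censoring.
- 600 patients, T = 10%, c = 20%: sudden death averages 4.14% by 1-KM against 4.01% by cumulative incidence. The two-curve sum averages 8.26% and exceeded total mortality in no run.
- 600 patients, T = 10%, c = 0: the two-curve sum averages 10.25% against a total of 9.99% and exceeded it in every run.
- 1400 patients, T = 10%, c = 20%: 4.14% against 4.02%. The larger sample does not shrink the gap.

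**The case against.** - **The censoring is not written down.** This stands. The plan says Kaplan-Meier and an unspecified survival analysis, and treatment of other-cause deaths is inferred. It is still what a Kaplan-Meier curve run for one cause does by default, and nothing in the plan points elsewhere.
- **A cause-specific Kaplan-Meier curve is not wrong in itself.** This also stands, if the curve is labelled as net risk. Censoring other causes is likewise the correct step when fitting cause-specific hazards. The plan gives no such label.
- **The effect is small.** At T of 5% or 10% with c = 20%, the bias is 0.03 or 0.13 percentage points. With 600 patients, simple binomial standard errors at 2% and 4% are sqrt(0.02 × 0.98/600) = 0.57 and sqrt(0.04 × 0.96/600) = 0.80 points. At such mortality, sampling error dominates. This stands and limits the severity. No test or decision rule depends on these curves, and the primary EF analysis is untouched.
- **A reader might infer that the planned components will sum to more than total mortality.** The documents do not support this. Non-cardiac deaths count in the aggregate but have no curve, so the two planned curves exceed the total only when non-cardiac deaths are very few.
- **A reader might take the 10% at 90 days in 1.1.1 as the competing mortality here.** It is total mortality, so it already includes sudden deaths. It comes from a 2006 Veterans Affairs population, and it covers the first 90 days, which most study patients will have survived before enrolling at about day 90.

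**Conclusion.** The point holds as a minor one. Separate Kaplan-Meier curves by cause, with no competing-risks method named, would by default overstate the actual cumulative risk of sudden and of non-sudden cardiac death. The direction follows from the estimator, given the inferred censoring. The size depends wholly on assumptions, since the documents give no one-year or cause-specific mortality for this cohort: it is negligible to small at 5-10% total mortality and becomes noticeable at 20% and above, under constant hazards and an even split of cardiac deaths.

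The claim about sums holds only for the complements taken over all causes, non-cardiac death included. It should not be made about the two curves that 8.3.6 plans.

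**What to change.** Amend 8.3.6 along these lines:

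- All-cause mortality is estimated by Kaplan-Meier.
- Sudden cardiac, non-sudden cardiac and non-cardiac death are each estimated by the Aalen-Johansen cumulative incidence function, with the other causes as competing events, so that the three sum to total mortality.
- Effects of baseline characteristics and EF recovery status on death by cause are estimated through cause-specific hazards.
- Any cause-specific Kaplan-Meier curve that is kept is labelled as net (hypothetical) risk.

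The cost is a few lines of wording and standard software. The cause categories are already collected, so no new data are needed.

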## 8.3.7 Safety Endpoint- Complication data from WCD or ICD

Descriptive statistics will be used to analyze the incidence of complications from WCDs and ICDs in this population. This will include inappropriate treatments, as well as any other complications that may lead to hospitalizations or death.

#### 8.4 Statistical Methods

All analyses have been described elsewhere in the protocol.

### 8.5 Additional Statistical Analysis

NA

## 8.6 Handling Missing Data

Due to the observational nature of this study and the long term repeated collection of data, missing data is to be expected.

#### 8.6.1 Sources of Missing Data

- 8.6.1.1 Retrospective data (i.e. collection of past medical history).
- 8.6.1.2 Patients who are lost to follow up.
- 8.6.1.3 Patients being un-timely in scheduling their follow-up appointments.

## 8.6.2 Preventing Missing Data

- 8.6.2.1 Collect only critical data elements that are routinely collected
- 8.6.2.2 All attempts to maintain contact with the patient should be made by study personnel to assure that lost patients are kept to a minimum. This may involve phone calls or patient support groups. Multiple phone numbers/contacts for each patient should be collected. Multiple reminders of upcoming visits should be made.
- 8.6.2.3 Generous windows of time (± 14 days) for follow-up appointments have been employed.
- 8.6.2.4 Routine site monitoring with data verification will occur throughout the study.

#### 8.6.3 Handling missing data

- 8.6.3.1 Loss to follow-up has been anticipated in the sample size calculation.
- 8.6.3.2 Missing data will not be replaced by any algorithm.

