#### 8.1.1 Statistical design used for sample size calculation

This dataset will be used evaluate among all patients, if more than 5% of them will experience EF improvement between 90 and 180 days ( $n_5/n > 5\%$ ).

To calculate the number of samples (n), we first calculated  $n_4$ , then calculated n based on the following formula:

$$n = \frac{n_4}{P_{followup2}} * \frac{1}{p_{wcd}} * \frac{1}{P_{followup1}}$$

where  $p_{wcd}$  is the percentage of patients who will wear WCD beyond 90 days ( $n_1/(n_1+n_2+n_3)$ ,  $p_{followup1}$  and  $p_{followup2}$  are the percentage of patients with proper follow up from 0 to 90 days and from 90 days to 180 days respectively, both of the them equals to 0.85 (1-0.15=0.85).

To calculate sample size for  $n_4$ , we performed superiority test. The statistical hypothesis to be tested is:

[figure not shown]
$$H0: P \le P_0 + \delta \text{ vs } H1: P > P_0 + \delta$$

The sample size of superiority test is calculated as the following formula:

$$n_4 = p(1-p) \left( \frac{Z_{1-\alpha} + Z_{1-\beta}}{p - p_0 - \delta} \right)^2$$

where p is the actual proportion of patients who will have EF improvement ( $n_5/n_4$ ).  $p_0$  is the baseline proportion, and specified as 0.001 (close to 0).  $\delta$  is the test margin, since the hypothesis is that more than 5% of them will experience EF improvement between 90 and 180 days ( $n_5/n > 5\%$ ),  $\delta$  depends on  $p_{wcd}$  as  $\delta = 0.05/P_{wcd}$ . We also specify  $\alpha$  as 0.05,  $\beta$  as 0.1

As shown in figure above, sample size (n) depends both on p, the actual proportion of patients who will have EF improvement (p=n5/n4) and  $p_{wcd}$ , the percentage of patients who will wear WCD beyond 90 days ( $p_{wcd} = n_1/(n_1+n_2+n_3)$ ).In this study, we specify  $\alpha$  as 0.05,  $\beta$  as 0.1. We predict that about 1/3 patients will have continued WCD wear from 90 to 180 days; and actual proportion of WCD patients at 90 days to have further EF improvement is 23%. In this case, we plan to prescribe WCD to 868 patients (initial registry sample size), in order to have approximately 738 patients eligible for the study at day 90. If mid-study analysis shows continued WCD use to be far out of 1/3, then sample size will be re-adjusted as necessary.

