## 8.3 Endpoint Assessment

## 8.3.1 Primary Endpoint – LVEF recovery and GDMT

Descriptive or summary statistics of serial EF measurements will be used to analyze the rate of recovery of ventricular dysfunction following discharge. For example, the means of EF at 180 days will be compared to the means of EF at baseline and 90 days. The percentage of patients reaching the goal of EF>35% will be compared at 90 days and 180 days. Also, the time taken to reach EF>35% will be calculated for those who improve, and compared between groups (based on baseline characteristics). Individual patient EF measurements over time will be compared to determine whether common patterns arise in certain groups of patients (fast recovery/slow recovery, plateaued recovery/peaked recovery followed by decline). The influence of baseline characteristics on the potential for recovery will be evaluated.

Descriptive statistics will be used to assess the degree GDMT was reached at 90 and 180 days, and how GDMT relates to EF recovery. We will also assess how adherence to the GDMT regimen affects EF recovery and overall clinical improvement.

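### Visit-by-visit EF figures, no replacement of missing values and no rule for denominators or deaths let the 90- and 180-day recovery results rest on different patients

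*Combined protocol and SAP*

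**What the plan says.** Section 8.6.3 has two lines. The first is "Loss to follow-up has been anticipated in the sample size calculation"; the second is "Missing data will not be replaced by any algorithm". The allowance itself is in sections 8.1 and 8.1.1: "assuming ~15% lost follow up, 738 patients will have an EF measurement at day 90", and for the follow-up shares from 0 to 90 and from 90 to 180 days, "both of the them equals to 0.85 (1-0.15=0.85".

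For the primary endpoint, section 8.3.1 is descriptive. It says that "the means of EF at 180 days will be compared to the means of EF at baseline and 90 days" and that "The percentage of patients reaching the goal of EF>35% will be compared at 90 days and 180 days". It gives no denominator for either comparison. Section 8.4 adds only "All analyses have been described elsewhere in the protocol", and section 8.5 is marked not applicable.

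Under section 5.4.2, data already collected from withdrawn or lost patients stay in the analysis. Section 8.6.1 lists sources of missing data, and death is not among them.

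**The concern.** The primary question is a change over time: do at least 5% more patients recover between day 90 and day 180? A patient lost after day 90 contributes to the day-90 figure and not to the day-180 figure. If the lost patients differ in EF from those who stay, the difference between the two figures mixes change within patients with a change in who is measured.

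Missingness unrelated to EF cannot be taken for granted here. Section 1.3 reports, from a cited ICD trial in non-ischaemic cardiomyopathy, that patients whose EF improved had lower total mortality, and a patient who has died has no EF. Recovered patients may also stop attending, so the direction is not known in advance. Enlarging the sample for expected loss protects precision. It does not protect against this bias.

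**Working it through.** **Inputs.** Registry 868 and 15% loss per interval (sections 8.1, 8.1.1). One-third recovered by day 90 (section 2.1). One-third continuing the WCD, 23% of them improving, baseline proportion 0.001, one-sided alpha 0.05 (section 8.1.1). Hypothesised gain 5% (section 3.2.2).

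**The plan's own figure.** 868 × 0.85 = 737.8, which reproduces 738 with a day-90 EF. A further 15% loss removes 111, leaving 738 − 111 = 627 with a day-180 EF.

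**1. The visit-wise percentage when nobody changes.** At day 90, 738/3 = 246 patients have EF>35%, or 33.3%. Suppose every patient's status stays the same and a fraction r of the 111 lost patients had recovered. The observed day-180 percentage is (246 − 111r)/627.

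| Recovered among the lost (r) | Day-180 percentage | Apparent change |
|---|---|---|
| 0 | 246/627 = 39.2% | +5.9 points |
| 20% | 223.8/627 = 35.7% | +2.4 points |
| one-third | 209/627 = 33.3% | 0.0 points |
| 50% | 190.5/627 = 30.4% | −3.0 points |
| all | 135/627 = 21.5% | −11.8 points |

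Apart from rounding, the shift equals (0.15/0.85) × (1/3 − r). It does not depend on the number enrolled, so the revised cap of 600 leaves it unchanged.

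**2. The share newly recovered between day 90 and day 180.** The planning value is 0.23 × 1/3 = 7.67% of all patients. Take it as the observed share, with 15% missing at day 180.

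- No missing patient newly recovered: 0.0767 × 0.85 = 6.5%.
- Only WCD continuers can newly recover, and all the missing ones did: 6.5% + 15%/3 = 11.5%.
- Anyone not recovered at day 90 can, and all the missing ones did: 6.5% + 15% × 2/3 = 16.5%.

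**3. The sample-size test, worst case.** Continuers at day 90 number 738/3 = 246. This is a different group from the 246 recovered patients; both happen to be one-third. At 15% loss 37 are missing and 209 observed, of whom 0.23 × 209 ≈ 48 improve. The null bound is 0.001 + 0.05/(1/3) = 0.151. Counting all missing as not improved gives 48/246 = 19.5%, with an exact one-sided p of 0.036.

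**The case against.** The best defence is that the study is observational, section 8.3.1 is mostly descriptive, and the quantity behind the sample size is a within-patient proportion among WCD continuers. Section 8.3.1 also says that individual EF courses over time will be compared. On that within-patient proportion the planned conclusion survives even the worst case in step 3. This stands, and it limits the point: the exposure lies mainly in the visit-wise contrast and in the missing rule for deaths. It does not remove the point, because section 3.1 says the study tests a hypothesis of added recovery, and the comparisons written for the primary endpoint are the visit-wise ones.

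It is also true that the no-replacement line does not by itself force an observed-case analysis. A likelihood-based repeated-measures model replaces nothing and would comply with it. The difficulty comes from that line together with section 8.3.1 and the absence of any other method. The plan never says that the two visits will be analysed as unpaired groups; it leaves this open.

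A reader might go further in three ways that the documents do not support.

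- One might compound the two losses to about 28% (1 − 0.85²). The first loss occurs in the registry, before enrolment at day 90, so it concerns selection into the study and not missing day-180 EF in study patients.
- One might add the whole missing 15% to the 6.5% as an upper bound. Patients already above 35% at day 90 cannot newly recover, so that total is unattainable.
- One might conclude that dropout inflates the apparent gain. Step 1 shows that the sign depends on who is lost.

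**Conclusion.** The point holds for the visit-wise comparisons. With 15% loss after day 90, the change in the percentage recovered can lie anywhere from −11.8 to +5.9 points with no true change in any patient, a range that contains the 5-point gain under study. For the share newly recovered, the range is 6.5% to 11.5%, or to 16.5% on the wider definition; the lower end stays above 5%.

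The extremes are bounds, not predictions. They rest on the planning values: one-third recovered at day 90, one-third continuing the WCD, 23% improving and 15% loss. Section 8.1.1 reports that dropout before the registry exceeded prediction but gives no updated follow-up rate, so the actual loss after day 90 may differ. The plan does not show that the study would miss its 5% threshold, and that is not claimed here.

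**What to change.** In section 8.3.1, define the recovery share from day 90 to day 180 on one fixed set: all patients enrolled at day 90 who have a day-90 EF. Make it a within-patient change (not above 35% at day 90, above 35% at day 180), and count deaths before day 180 as not recovered. Analyse mean EF with a likelihood-based repeated-measures model that uses every available EF. Report deaths beside the modelled means, since such a model treats EF after death as merely unobserved.

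In section 8.6.3, replace the flat rule. For day-180 EF missing among survivors, allow multiple imputation or inverse-probability weighting based on baseline and day-90 EF, GDMT status and hospitalisations. Give best- and worst-case bounds and the observed-case result as sensitivity analyses.

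The cost is revised wording and a little more analysis work, with no new data collection. The stated share may turn out less favourable than the observed-case figure.
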